6.4.3 Malignancy

Immunosuppression is associated with increased risk of lymphoma and other malignancies, particularly skin cancers. Participants should be advised to avoid or limit unprotected exposure to sunlight and UV light. If evidence of lymphoproliferative disease emerges, work up will be guided by the institution's standard of care requirements. If malignancy (other than non-melanoma skin cancer) is diagnosed, study medications will be discontinued, and the participant will be treated according to standard of care per institutional requirements. If new non-melanoma skin cancer is found and fully treated with local procedures, the participant may continue in the trial as planned based on investigator discretion. Participants over the age of 50 should have age-appropriate cancer screenings at the investigator's discretion prior to enrollment and throughout the course of the study. For additional information, consult the American Cancer Society (ACS) reference below:

<http://www.cancer.org/healthy/toolsandcalculators/reminders/screening-recommendationsby-age>

6.4.4 Infections

Immunosuppression is associated with increased risk of infection. Individuals with active or chronic infections are excluded from the study. Participants will receive guidance recommending vaccinations be up-to-date according to local standards and lymphocyte counts will be monitored through the study. Participants will be followed closely for signs of infection at study visits, and between visits if needed. In the setting of infection, study medications may be withheld based on institutional practices or investigator judgment, for up to 2 weeks and then resumed at scheduled dose. Otherwise, refer to the guidelines in 6.5, Premature Discontinuation of Investigational Agent in the event of toxicity.

Additionally, low IgG levels are found in less than 10% of patients with SLE and are usually not associated with infection [73]. However significant drops in IgG have been seen with various immune-modulating medications and if

not carefully monitored may increase risk for serious infections and death [26, 43]. We will employ a safety mitigation strategy that was successfully employed in a study of Atacicept, the ADDRESS II trial [74]. At the Screening Visit, participants must have serum IgG levels ≥ 5 g/L. Immunoglobulin levels will be checked throughout the course of the study per Table 8.1 *Schedule of Events*. If at any time during the study these levels fall to < 4 g/L, study medication will be withheld with a retest at one week. If retest demonstrates recovery to ≥ 4.5 g/L, medication may be restarted. If not, another retest may be performed in another week. If IgG does not recover to ≥ 4.5 g/L after the second retest, study medication will be permanently withdrawn as per the guidelines in Section 6.5, *Premature Discontinuation of Investigational Agent*.

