- If the participant is deemed a Stage 2 treatment failure as defined in protocol Section 3.2, *Primary Endpoint*, and a corticosteroid injection is deemed insufficient and a new or increased lupus medication is required, then a blood sample for mechanistic studies will be drawn, Stage 2 study-provided medication will be stopped, and the new or increased lupus medication will be started outside of the study. The participant will not be eligible for Stage 3 but will be followed to Stage 2 Week 24 or 4 weeks \pm 10 days after the last dose of study-provided medication, whichever is later, before exiting the study. Participants who exit the study at Stage 2 Week 24 should complete all End of Study/Safety Follow-Up visit assessments at this time.

Participants who have not failed Stage 2 on or before the Stage 2 Week 24 visit will continue on Stage 2 study-provided medication through Stage 2 Week 48 or until treatment failure, whichever occurs first.

- If the participant is deemed a Stage 2 treatment failure after Stage 2 Week 24, then study-provided medication will be stopped. Prior to treatment with a corticosteroid injection or a new or increased lupus medication outside of the study, a blood sample for mechanistic studies will be drawn. The participant will return for an End of Study/Safety Follow-Up Visit 4 weeks \pm 10 days after the final dose of study-provided medication.
- Participants who have not failed Stage 2 on or before the Stage 2 Week 48 visit will return for an End of Study/Safety Follow-Up Visit 4 weeks \pm 10 days after the final dose of study-provided medication.

Severe lupus manifestations that are life-threatening or organ-threatening should prompt consideration for withdrawal from the study in order to enable maximal therapy with corticosteroids and other lupus medications. The ultimate decision on withdrawal should be left up to the clinical judgment of the investigator.

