6.5 Premature Discontinuation of Investigational Agent

Study participants who discontinue investigational agent prematurely but are willing and able to remain in the study and undergo evaluation per protocol will be encouraged to do so.

Study therapy may be paused for up to 2 weeks for infections, gastrointestinal abnormalities, HTN, decreased eGFR, hematologic abnormalities and hepatic abnormalities as detailed in Section 6.4, *Toxicity Prevention and Management*.

Study therapy may be prematurely discontinued for any participant for any of the following reasons:

1. Participant decision.
2. Determination of unacceptable toxicity, including but not limited to:
 - a. Gastrointestinal abnormalities that do not resolve after study medications are withheld for up to 2 weeks as outlined in Section 6.4.5, *Gastrointestinal abnormalities*;
 - b. HTN that does not resolve after study medications are withheld for up to 2 weeks as outlined in Section 6.4.6, *Hypertension*;
 - c. Decreased eGFR that does not resolve after study medications are withheld for 2 weeks as outlined in Section 6.4.7, *Decreases in eGFR*;
 - d. Hematological Abnormalities that do not resolve after study medications are withheld for up to 2 weeks as outlined in Section 6.4.9, *Hematological Abnormalities*;
 - e. Hepatic Abnormalities that do not resolve after study medications are withheld for up to 2 weeks as outlined in Section 6.4.10, *Hepatic Abnormalities*;
 - f. Grade 4 Leukopenia (WBC < 1000/mm³, equivalent to 1.0 x10⁹/L); and
 - g. Grade 4 Neutropenia (Neutrophils < 500/mm³, equivalent to 0.5 x10⁹/L);
3. Treating physician determination of any condition that warrants withdrawal of study medication.
4. Any condition that in the opinion of the DAIT Medical Monitor warrants withdrawal of study medication.
5. The participant becomes pregnant.
6. The participant develops a malignancy (other than non-melanoma skin cancer).
7. Treatment failure, as defined in Section 3.5.1, *Clinical Endpoints* including corticosteroid injection(s) or treatment with a new or increased lupus medication.
8. Toxicity or Infection (see Section 6.4, *Toxicity Prevention and Management*):
 - a. If study medication is withheld for more than 14 sequential days due to suspected toxicity or infection.
 - b. Grade 4 infection.

7 Other Medications

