EULAR/ACR 2019 Criteria for SLE	X															
PGA	X	X	X	X	X	X	X	X	X	X	X	X	X	X	X	X
BILAG 2004	X	X	X	X	X	X	X	X	X	X	X	X	X	X	X	X
Hybrid SLEDAI	X	X	X	X	X	X	X	X	X	X	X	X	X	X	X	X
SELENA-SLEDAI Flare Index and Thanou Modified Flare Index	X	X	X	X	X	X	X	X	X	X	X	X	X	X	X	X
LFA-REAL-CLINRO™	X	X	X	X	X	X	X	X	X	X	X	X	X	X	X	X
CGI-I (CGI-C & CGI-S)	X	X	X	X	X	X	X	X	X	X	X	X	X	X	X	X
Assessment of Primary Endpoint ^F			X ^D							X ^{D,E,F}						
Disease and SLE Treatment Status										X ^E	X	X ^{D,E,F}				
Tender and Swollen Joint Count Assessment	X	X	X	X	X	X	X	X	X	X	X	X	X	X	X	X
Participant Reported Outcomes^Q																
SF-36	X	X	X	X	X	X	X	X	X	X	X	X	X	X	X	X
PGI-I (PGI-C & PGI-S)	X	X	X	X	X	X	X	X	X	X	X	X	X	X	X	X
LFA-REAL-PRO™	X	X	X	X	X	X	X	X	X	X	X	X	X	X	X	X
Local Laboratory Assessments^B																
Urine Pregnancy ^G		X	X	X	X	X	X	X	X	X	X	X	X	X	X	X
SARS-CoV-2 Antigen Testing	X ^R	X												X ^M		
TB Testing (Quantiferon Gold) ^H	X															

	STAGE 1 (up to 4 weeks)	STAGE 2 (up to 52 weeks)													End of Study
Visit Number	SCRN	STG2-1	STG2-2	STG2-3	STG2-4	STG2-5	STG2-6	STG2-7	STG2-8	STG2-9	STG2-10	STG2-11	STG2-12	STG2-13	
Description	Screening	Random- ization	Week 4	Week 8	Week 12	Week 16	Week 20	Week 24 ^P	Week 28	Week 32	Week 36	Week 40	Week 44	Week 48	
Visit Window	-28 Days	Day 0 ± 24 hours	± 5 days	± 5 days	± 5 days	± 5 days	± 5 days	± 5 days	± 5 days	Early Termination Unscheduled					
Central Laboratory Assessments^B															
Hematology (CBC with differential)	X	X	X	X	X	X	X	X	X	X	X	X	X	X	X
Blood Chemistry	X	X	X	X	X	X	X	X	X	X	X	X	X	X	X
Lipids (triglycerides and cholesterol)	X														X X ^c X
Urinalysis (dipstick, microscopic, spot protein-creatinine)	X	X	X	X	X	X	X	X	X	X	X	X	X	X	X
TBNK Trucount	X ^s														
Serum Pregnancy ^G	X														
Anti-dsDNA, C3, C4	X	X	X	X	X	X	X	X	X	X	X	X	X	X	X
Immunoglobulin G	X				X			X							X X X ^c X
Autoantibodies (ANA, ENA Panel, Anticardiolipin)	X				X			X							X X X ^c X
HIV Testing	X														
Hepatitis B Surface Antigen and Core Antibody Screening (with viral load if indicated)	X														
Hepatitis C Antibody (with viral load if indicated)	X														
Mechanistic Assessments^B															
Whole Blood/PBMC/Plasma	X	X	X	X	X	X	X	X	X	X	X	X	X	X	X
Serum	X	X	X	X	X	X	X	X	X	X	X	X	X	X	X

	STAGE 1 (up to 4 weeks)	STAGE 2 (up to 52 weeks)													End of Study		
		SCRN	STG2-1	STG2-2	STG2-3	STG2-4	STG2-5	STG2-6	STG2-7	STG2-8	STG2-9	STG2-10	STG2-11	STG2-12	STG2-13		

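### The IgG hold rule is written to apply throughout the study, but Table 8.1 schedules no routine IgG test between Week 24 and Week 48, while participants are still on Stage 2 drug

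*Combined protocol and SAP*

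**What the plan says.** Section 6.4.4 (Infections) gives low IgG its own safety rule. Entry requires at least 5 g/L. On monitoring it says "Immunoglobulin levels will be checked throughout the course of the study per Table 8.1". On action it says "If at any time during the study these levels fall to < 4 g/L, study medication will be withheld with a retest at one week". Drug may restart once IgG is back to 4.5 g/L or more. If that level is not reached, "after the second retest, study medication will be permanently withdrawn as per the guidelines in Section 6.5".

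Section 3.1.2 says that participants who have not failed by Week 24 "will continue on Stage 2 study-provided medication through Stage 2 Week 48", or until treatment failure if that comes first.

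The "Immunoglobulin G" row of Table 8.1 is marked at Screening, Week 12 and Week 24, and then again only at the right-hand end of the table. The cells for Weeks 28 to 44 are empty. The mark for unscheduled visits carries footnote C, which limits the test to cases where it is clinically indicated. Table 8.2 places IgG in Stage 3 at re-randomization (if not already collected), Week 12 and Week 24.

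**The concern.** The rule is triggered by a laboratory value, so it protects a participant only if the value is measured while there is still drug to withhold. Section 6.4.4 presents the rule as continuous. The schedule it points to stops routine testing halfway through the longest treatment course in the trial.

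The other laboratory hold rules are matched to the visit schedule. eGFR is evaluated at each visit (Section 6.4.7), the blood count at each visit (Section 6.4.9) and liver tests every 4 weeks (Section 6.4.10). IgG after Week 24 of Stage 2 is the exception.

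Section 6.4.4 itself links IgG drops that are not carefully monitored to serious infection and death. It also says that low IgG in lupus is usually not accompanied by infection, so a fall may give the investigator no reason to order a test. The people affected include those with the longest Stage 2 exposure to MMF.

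**Working it through.** There is no power or alpha figure to reproduce. The check is a reading of the schedule, a length of gap and a head count.

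**1. Which visits have IgG.** Table 8.1 has 17 visit columns: Screening, Randomization, Weeks 4 to 48 in steps of 4, Early Termination, Unscheduled and Safety Follow-Up. The IgG row reads "Immunoglobulin G X X X X X X ^c X", which is seven marks. By cell position, the first three fall in column 1 (Screening), column 5 (Week 12) and column 8 (Week 24). The last four are run together at the right edge. They fit Week 48, Early Termination, Unscheduled (footnote C) and Safety Follow-Up. Columns 9 to 13 (Weeks 28 to 44) hold no mark.

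**2. Cross-check on a table read by machine.** The clinical draw row gives 19 mL at Weeks 12, 24 and 48, and 11 mL at each of Weeks 28, 32, 36, 40 and 44. That matches the reading above, with two limits:
- The autoantibody panel has the same marks as IgG, so the 8 mL difference (19 − 11) does not isolate IgG.
- At Weeks 12 and 24 the printed visit total is 60 mL, although 19 + 49 = 68. At Weeks 28 to 44 the rows agree (11 + 49 = 60), so this slip does not touch the visits in question.

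**3. Which of these tests can start a hold.** The Week 48 result comes at the end of Stage 2 dosing. The Safety Follow-Up sample is taken after drug has stopped, and the Early Termination sample when the participant is leaving the study. None of the three leaves Stage 2 drug to withhold.

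**4. Length of the gap.**
- Week 24 to Week 48: (48 − 24) × 7 = 168 days. With ± 5 days at each end, 158 to 178 days.
- Week 12 to Week 24: (24 − 12) × 7 = 84 days.
- Stage 3: re-randomization to Week 12, and Week 12 to Week 24, 12 weeks each.

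The gap is twice the interval used elsewhere on treatment.

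**5. Who enters the period.** Section 13.7 assumes 60 per arm, with Week 24 survival free of failure of 10–15% on placebo and 35–50% on MMF. Permanent discontinuation counts as treatment failure (Section 3.5.1), so a participant free of failure at Week 24 is still on drug.
- Placebo: 60 × 0.10 = 6 to 60 × 0.15 = 9.
- MMF: 60 × 0.35 = 21 to 60 × 0.50 = 30.
- Total: 6 + 21 = 27 to 9 + 30 = 39 of 120.

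**The case against.** The strongest reply is that the two passages do not contradict each other. Section 6.4.4 adopts the schedule of Table 8.1 by name, and "If at any time during the study these levels fall to < 4 g/L, study medication will be withheld" says what to do with a low value when one is found; it sets no test frequency. How often to test is a design choice. Participants are still seen every 4 weeks and watched for infection, and they had tests at Weeks 12 and 24. The same section puts low IgG at under 10% of lupus patients. All of that is fair. It does not explain why a rule described as running through the whole study has five consecutive on-treatment visits without its test. Nor does the precedent cited in Section 6.4.4 settle the matter: the reference list titles that atacicept trial a twenty-four-week study.

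Three stronger readings might be inferred, and the documents support none of them.
- **That the rule cannot operate at all after Week 24.** A low Week 24 result would start a hold and weekly retests inside the period. Section 8.1.6 lets the investigator call an unscheduled visit, at which Table 8.1 allows IgG for cause.
- **That everyone who continues has 24 weeks without a routine test.** That is the maximum. Drug stops at treatment failure, so later failures have a shorter gap, and 6 to 9 of the 27 to 39 are on placebo.
- **That Section 6.5 disables the rule by not naming IgG.** Its pause sentence, "Study therapy may be paused for up to 2 weeks for infections, gastrointestinal abnormalities, HTN, decreased eGFR, hematologic abnormalities and hepatic abnormalities", names infections and refers to Section 6.4, where the IgG rule sits under Infections. Its toxicity list is expressly not exhaustive, and it covers holds of more than 14 days for suspected toxicity or infection.

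**Conclusion.** The concern holds in a limited form. After Week 24, no routine IgG test can newly trigger the hold rule until Week 48, when Stage 2 dosing ends. Detection in between rests on the Week 24 result or on a for-cause test, and a fall without symptoms could go undetected for up to 24 weeks on drug, against 12 weeks elsewhere on treatment. On the plan's assumptions, 27 to 39 participants enter this period, 21 to 30 of them on MMF.

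This rests on the reading of a machine-extracted table with merged right-hand cells, which the draw volumes support, and on the survival rates assumed in Section 13.7. The documents give no rate of IgG below 4 g/L on MMF, so the number of falls that would be missed cannot be estimated. It is a safety-monitoring gap that is worth closing because closing it is cheap. It does not affect the primary analysis at Week 24.

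**What to change.** Reconcile Section 6.4.4 with Table 8.1 in one of two ways:
- make the schedule support the rule as stated for as long as participants remain on Stage 2 drug after Week 24; or
- say in Section 6.4.4 that routine IgG monitoring lapses after Week 24, and give the reason.

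The test interval and any hold or stop rule are for the sponsor to set. While editing, Section 6.4.4 could also cite Table 8.2, which holds the Stage 3 IgG tests. Section 6.5 needs no change beyond optional wording that names IgG.

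The cost is small. Participants already attend and give 60 mL at each of the five visits. If a visit rose to the 19 mL clinical draw used at the IgG visits, its total would be 19 + 49 = 68 mL; three such visits within 8 weeks would come to 3 × 68 = 204 mL, against the limit of 550 mL. Each added time point means one more assay for at most 27 to 39 participants on the plan's assumptions, plus the text and table edits.

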6.4.4.1 SARS-CoV-2 Infections

Participants are encouraged to receive full COVID-19 vaccination per CDC guidelines. Participants will be tested for SARS-CoV-2 as part of screening as mandated by the entry criteria and throughout the study as clinically indicated. Assessment, prophylaxis, and treatment for infection will be guided by standard of care per institutional requirements; however, individuals participating in ALE10 are at high risk for SARS-CoV-2 infection. Per standard recommendations, a participant with mild to moderate COVID-19 symptoms should be evaluated for treatment with an FDA authorized or approved COVID-19 treatment as soon as possible following confirmation of the infection and within 10 days of symptom onset. Additionally, any participant who has close contact with a SARS-CoV-2 infected individual should be evaluated as soon as possible after exposure. Additional FDA Approvals and EUAs are anticipated for the prevention and treatment of SARS-CoV-2. Site investigators are expected to keep abreast of these approvals and authorizations in order to advise ALE10 trial participants about optimal prevention and treatment. NIH COVID-19 treatment guidelines can be found here:

<https://www.covid19treatmentguidelines.nih.gov/>.

6.4.5 Gastrointestinal Abnormalities

Gastrointestinal side effects including nausea and diarrhea are associated with MMF use. If these symptoms exacerbate without other likely explanation, study medications may be withheld for up to 2 weeks and resumed at the scheduled dose. Otherwise, refer to the guidelines in Section 6.5, *Premature Discontinuation of Investigational Agent* in the event of toxicity.

6.4.6 Hypertension

Voclosporin may be associated with increased risk of HTN [75]. Individuals with uncontrolled HTN are excluded from participation in the study (See Section 4.3, *Exclusion Criteria* number 7 for additional detail). During the study, blood pressure will be evaluated at each study visit, including once 2 weeks after initiating Stage 3 study therapy. Clinically concerning elevated blood pressure should be managed with antihypertensive therapy. In the event of HTN associated with a SAE or a Grade 3 or above AE that is possibly or definitely related to study medication, study medications may be withheld for up to 2 weeks. If the AE does not resolve down to Grade 2 or below after 2 weeks of withholding medication, study medication should be discontinued. If the AE improves to grade 2 or below but increases again to grade 3 once study medication is reinstated then study product should be discontinued permanently.

6.4.7 Decreases in eGFR

For voclosporin use, regular monitoring of eGFR is recommended per the Investigator Brochure, every 2 weeks for first month then every 4 weeks thereafter. Clinically significant decreases have been observed with voclosporin plus

MMF as well as for MMF alone. For this study, individuals with eGFR < 45 mL/min per 1.73 m² at screening are excluded. eGFR will be evaluated at each study visit. It will also be assessed at a Stage 3 Week 2 Safety Check Visit two weeks after initiating Stage 3 therapy. The most recent assessment of eGFR before the Stage 3 Re-randomization Visit should be used as baseline for Stage 3 Week 2 eGFR assessment.

If eGFR < 60 mL/min per 1.73 m² and is reduced from Stage 3 baseline by 20-30%, reduce dose by one capsule BID (total of 2 capsules BID). Reassess eGFR in 2 weeks, and if it is still reduced by > 20% from baseline, reduce dose to 1 capsule BID. If eGFR < 60 mL/min per 1.73 m² and reduced from Stage 3 baseline by > 30%, withhold voclosporin for 2 weeks, then reassess and consider re-initiating at 1 capsule BID if eGFR is > 80% of baseline.

6.4.8 Glucose and Diabetes

The development of new-onset diabetes is an important, recognized effect of CNI inhibitors. In voclosporin clinical trials, the incidence of AEs related to diabetes and glycemic control was low and similar in both treatment groups, indicating that there is no increase in these types of events with voclosporin treatment. Uncontrolled diabetes may be excluded from the trial per investigator discretion according to the inclusion/exclusion criteria set in Section 4, *Selection of Participants*.

6.4.9 Hematological Abnormalities

Individuals meeting thresholds for exclusionary levels of neutrophils, WBC, platelets, and hemoglobin at screening are excluded from the study (See Section 4.3, *Exclusion Criteria* number 8 for additional detail). To monitor potential hematological toxicity, the participants will have a complete blood count at each visit. If any of the following develop without explanation and persist after a repeat check in one week, then study medications will be held for one week and the test repeated:

- neutropenia (neutrophils < 800/mm³, equivalent to 0.8 x10⁹/L),
- leukopenia (WBC < 1500/mm³, equivalent to 1.5 x10⁹/L),
- thrombocytopenia (platelets < 40,000/mm³, equivalent to 40 x10⁹/L), or
- anemia (hemoglobin < 7.0 g/dL).

Study medication may be held up to 2 weeks while the abnormality is monitored weekly for recovery. If recovery to screening value occurs then study medication can be resumed. Otherwise, refer to the guidelines in Section 6.5, *Premature Discontinuation of Investigational Agent* in the event of toxicity. If participants have symptomatic complications from the hematological derangements, this should be treated according to standard of care per institutional requirements.

6.4.10 Hepatic Abnormalities

Individuals with AST or ALT > 2.5x ULN at screening are excluded from the study. Liver function tests will be checked every 4 weeks for signs of hepatic toxicity. If transaminases exceed 3x ULN without explanation, then study medications will be held for up to 2 weeks, and the abnormality followed weekly for resolution to screening value. Should resolution occur within 14 days, the study medication may be resumed. Otherwise, refer to the guidelines in 6.5, *Premature Discontinuation of Investigational Agent* in the event of toxicity.

